Date of outcome (in AD): / / (YYYY/MM/DD)	Weeks and days of pregnancy () weeks () days	Result	 Miscarriage	⇒ Specify details in the course field.
			 Abortion	⇒
			 Live birth	⇒ Specify details regarding delivery(ies) and
			 Stillbirth	⇒ newborn(s) in 14 and 15.

14. Details of delivery

 Natural childbirth  Cesarean section  Vacuum extraction/forceps delivery	Did she have heavy bleeding during labor (≥ 500 mL)?  No  Yes \Rightarrow () mL of bleeding	How long was she in labor? () hours and () minutes
Reason(s) for delivery other than natural childbirth: ()		

Did she have any abnormalities during labor? No Yes ⇒ If yes, specify the details (including treatment[s] given).
(Abnormal changes in blood pressure, cardiopulmonary arrest, weak/excessively strong contraction, coiling of the umbilical cord, amniotic fluid embolism, inversion of the uterus, maternal injury, maternal death, IVC, etc.)

Cardiotocometer (monitor) result (not compulsory)

No abnormality found Early deceleration Late deceleration Variable deceleration Other ()

111

Information regarding the newborn

15 Newborn

10. Newborn			
 Normal  Abnormal (live birth)  Stillbirth \Rightarrow Autopsy performed?			
		 Yes  No	
  Congenital anomaly or abnormality		 Birth trauma	
		Placental weight: () mL () g	
		Did she have turbid amniotic fluid?  Yes  No	
		Did her baby stay in the NICU?  No  Yes	

Sex	Height cm	Body weight g	Head circumference cm	Chest circumference cm	Apgar score 1-min score 5-min score	Blood pH (Blood from the head or cord blood) pH()
 Male						
 Female						

If any additional information is available, please enter it on page 3. (Please also attach copies if any related documents are available.)

IV.	Courses and other notices	
Reporter information		
16. Study site and contact information (Phone) Signature of the investigator:	17. Date of signature (in AD) YYYY/MM/DD	
Remarks (section for the sponsor only)		
18. Date of receipt of information (in AD): YYYY/MM/DD		
19. Name, department, and company: Mitsubishi Tanabe Pharma Corporation		
Please fill out this form and send it to Mitsubishi Tanabe Pharma Corporation by facsimile.

1 INTRODUCTION

This statistical analysis plan (SAP) is based on the final protocol (01.00.00000) dated 9-JUN-2022. The plan covers statistical analysis, tabulations and listings of the study data to investigate the efficacy and safety.

Any statistical analysis details described in this document supersede any description of statistical analysis in the protocol.

2 STUDY OBJECTIVE AND ENDPOINTS

2.1 Study Objective(s)

Primary objective:

To evaluate the long-term safety of 105 mg of oral edaravone administered once daily for 10 of the 14 days followed by a 14-day rest period. The study will last until the earlier of the date when the oral edaravone becomes commercially available for prescription at each site or August 31, 2023.

Exploratory objective:

To evaluate the efficacy of oral edaravone 105 mg once daily for 10 of the 14 days, followed by a 14-day rest period. The study will last until the earlier of the date when the oral edaravone becomes commercially available for prescription at each site or August 31, 2023.

Subjects participating in the study will be offered the opportunity to continue taking oral edaravone.

2.1.1 Primary Safety Assessment(s)

- (1) Adverse events (AEs) and adverse drug reactions (ADRs)
- (2) Physical examination, including neurological examination
- (3) Body weight
- (4) 12-lead ECG
- (5) Vital signs (heart rate, respiratory rate, systolic/diastolic blood pressure and axillary, oral or tympanic temperature [the method should be consistent throughout the study])
- (6) Safety laboratory tests (hematology, blood biochemistry, urinalysis, pregnancy test)
- (7) Columbia Suicide Rating Scale (C-SSRS)

Statistical Analysis Plan
Protocol No. MT-1186-A-301

Mitsubishi Tanabe Pharma Corporation

2.1.2 Exploratory Assessment(s)

- (1) ALSFRS-R score at each time of evaluation
- (2) Presence or absence of death, tracheostomy, or constant use of an assisted ventilator
(23 hours or more per day)
(If applicable, date of onset)

3 STUDY DESIGN

3.1 Phase and Type of the Study

Phase of the study : Phase III

Type of the study : Interventional

3.2 Study Design

3.2.1 Overall design of the Study

This is a multicenter, open-label, continuous safety trial (Phase III). The study was conducted to evaluate the long-term safety of 105 mg of oral edaravone administered once daily for 10 of the 14 days followed by a 14-day rest period until the earlier of the date when the oral edaravone becomes commercially available for prescription at each site or August 31, 2023.

Subjects who will complete Week 96 of Study MT-1186-A03 or Week 48 of Study MT-1186-A04 and meet eligibility criteria will be enrolled in this study (MT-1186-A-301). Subjects will receive oral edaravone once daily continuously after an overnight fast, and will have their next meal (breakfast, etc.) at least 1 to 2 hours after edaravone administration. A cycle consists of 28 days (10 days of study drug out of 14 days followed by 14 days of rest).

The cycle will be repeated every 28 days (10 days of study drug administration followed by a 14-day rest period). Subjects who discontinued the study will complete the Early Termination (ET) procedure within 7 days of discontinuation.

After the date of marketing approval in Japan, the clinical trial will be regarded as a post-marketing clinical study, and subjects participating in this study will be offered the opportunity to continue taking the drug.

Statistical Analysis Plan
Protocol No. MT-1186-A-301

Mitsubishi Tanabe Pharma Corporation

3.3 Schedule of Study Procedures

Examination/Observation		Open-label administration period	
Weeks (Tolerable range)		Day 1 (x): Common to Week 96 of Study MT-1186-A03 or Week 48 of Study MT- 1186-A04, and no repeat assessments/tests for this study.	24 (± 7D)
Cycle	1	7	
Assessment	1	2	3
Obtaining Consent	X		
Eligibility Criteria	X		
Demographic characteristics ^b	X		
Vital signs ^c	(X)	X	X
Vital signs measurement on standing	(X)	X	X
Pregnancy test (urine)	X	X	X
Detailed physical examination ^{d1}	(X)		X
Routine physical examination ^{d2}		X	
12-Lead ECG ^e	(X)	X	X
Weight	(X)	X	X
Death, tracheostomy, or constant use of an assisted ventilator ^f	(X)	X	X
Hematology ^g	(X)	X	X
Blood biochemistry tests ^h	(X)	X	X
Urinalysis ⁱ	(X)	X	X
Dispensing edaravone ^j	X	X	
ALSFRS-R	(X)	X	X
C-SSRS	(X)	X	X
Assessment of medication compliance ^k	(X)	X	X
Adverse events	(X)	X	X

Abbreviations: D = day, ECG = electrocardiogram, C-SSRS = Columbia Suicide Rating Scale, ALSFRS-R = Amyotrophic Lateral Sclerosis Functional Rating Scale-Revised, EOS = end of study, ET = early termination

a. Subjects who discontinue the study will complete the ET procedure within 7 days of discontinuation. If the investigational drug is discontinued, the site should follow up the subject by telephone as long as possible.

b. Demographic characteristics include age, sex, race, and ethnicity.

Statistical Analysis Plan

Protocol No. MT-1186-A-301

Mitsubishi Tanabe Pharma Corporation

- c. Vital signs include systolic/diastolic blood pressure, heart rate, respiratory rate, and axillary, oral, or tympanic temperature.(The same method should be used throughout the study.)
- d. Physical Examination:
 - 1. The detailed physical examination evaluates the abdomen, cardiovascular system, general condition, head, eyes, ears, nose, throat, lymph nodes, musculoskeletal system, neck, nervous system, skin and respiratory system, and other major body parts and organs.
 - 2. The usual physical examination evaluates the abdomen, cardiovascular system, general condition, respiratory system, nervous system, and other major body parts and organs.
- e. The ECG should measure the following: R wave-R wave (RR) interval, heart rate, QRS, QT, Bazett corrected QT interval (QTcB) and Fridericia corrected QT interval (QTcF). The 12-lead ECG should be measured after the subject has rested in the supine position for at least 5 minutes. The investigator (or subinvestigator) comprehensively evaluates the ECG for safety and reports the ECG record as "normal", "clinically significant abnormality (CS)" or "clinically non-critical abnormality (NCS)". Clinically significant abnormalities are reported as AEs.
- f. The event is death, tracheostomy, or constant use of an assisted ventilator (≥ 23 hours/day).
- g. The followings should be measured: red blood cell count, hemoglobin, hematocrit, white blood cell count, and platelet count.
- h. The followings should be measured: albumin, total protein, aspartate aminotransferase (AST), alanine aminotransferase (ALT), lactate dehydrogenase (LDH), alkaline phosphatase (ALP), and total bilirubin, phosphatase), total bilirubin, direct bilirubin, gamma glutamyl transferase (GGT), CK, total cholesterol, triglycerides, BUN, bicarbonate, serum glucose, serum creatinine, uric acid, sodium (Na), potassium (K), chlor (Cl), and Calcium (Ca).
- i. The followings should be measured: protein, glucose, occult blood, urobilinogen, leukocytes, and bilirubin.
- j. 105 mg of oral edaravone administered once daily for 10 of the 14 days followed by a 14-day rest period until the earlier of the date when the oral edaravone becomes commercially available for prescription at each site or August 31, 2023. Edaravone should be administered after an overnight fast, and the next meal, such as breakfast, should be taken at least 1 to 2 hours after edaravone administration.
- k. Medication compliance will be assessed at each visit by site staff.

3.4 Sample Size

Approximately 30 subjects in total

Approximately 30 subjects who have completed Week 96 of Study MT-1186-A03 or Week 48 of Study MT-1186-A04 may be enrolled. The total number of subjects enrolled will depend on the number of subjects who have completed Week 96 of Study MT-1186-A03 or Week 48 of Study MT-1186-A04 and who are eligible and agree to participate in this continuation study.

4 PLANNED ANALYSIS

4.1 Final Analysis

This SAP will be finalized before database lock. Final data analysis will be performed after database lock.

5 ANALYSIS POPULATIONS

Safety analysis set (SAF)

The SAF is defined as all subjects enrolled in the study who received at least 1 dose of oral edaravone. All efficacy and safety analyses will be performed for the SAF.

6 STATISTICAL CONSIDERATIONS

6.1 Descriptive Statistics

Continuous data will be summarized descriptively using the number of subjects in the analysis set (N), the number of observations (n), mean, SD, median, minimum and maximum. Categorical data will be summarized using frequency counts and percentages. The denominator for the percentages will be the total number of subjects in the analysis population applied, unless otherwise specified.

7 DATA CONVENTIONS

As a result of DRM held on 20 Sep, no subjects are excluded from the SAF. Refer to the minutes for details.

7.1 Analysis Variable Definitions

7.1.1 Study Subjects

7.1.1.1 Study Drug Exposure

(1) Duration of exposure

Duration of exposure (day) = the last day of oral edaravone administration in this study – the first day of oral edaravone administration in this study + 1

If the date of the last or the first administration is indeterminate, the exposure period is not calculated.

Non-compliance and interruption are not taken into account for the calculation of duration of exposure.

7.1.2 Efficacy Evaluation

7.1.2.1 ALSFRS-R score

A questionnaire used to assess the impact of ALS. The physical function of the subject is evaluated for 12 daily activities.

ALSFRS-R domains Score:

- Bulbar function = total of items 1 to 3
- Limb function = total of items 4 to 9
- Fine motor function = total of items 4 to 6
- Gross motor function = total of items 7 to 9
- Respiratory function = total of items 10 to 12

If there is missing score data in an item, the score of domains calculated using the item will be missing.

7.1.3 Safety Assessments

7.1.3.1 Adverse Events

Adverse events will be coded according to the MedDRA version 25.0.

(1) Treatment Emergent Adverse Events/ Treatment Emergent Serious Adverse Events (TEAEs/TEsAEs)

An AE/SAE is classified as treatment emergent if it newly occurred after the first dose of investigational product or if a pre-dose event increases in severity following the first dose of investigational product.

(2) Adverse Drug Reaction

A TEAE is considered “adverse drug reaction” if it has been assessed as having a “reasonable possibility” in relationship to the investigational product.

(3) Time to Adverse Events

Time to Adverse Events occurrence (days) = AE start date – date of first administration in this study + 1

If the date of onset of an adverse event or the first administration is indeterminate, time to adverse events occurrence is not calculated.

(4) Duration of Adverse Events

Duration of Adverse Events (days) = AE stop date – AE start date + 1

If the adverse event is ongoing at the end of study, duration of adverse events is not calculated.

7.1.3.2 Laboratory Tests

(1) Clinically relevant values flag

Clinically relevant values flag will be attached to the values out of normal range. (L=Lower than normal range, H=Higher than normal range or A=Abnormal).

7.1.3.3 12-Lead ECG

(1) Criteria for pre-defined limit

12-lead ECG:

- QTcF > 500 msec
- 500 >= QTcF > 480 msec
- 480 >= QTcF > 450 msec

Statistical Analysis Plan
Protocol No. MT-1186-A-301

Mitsubishi Tanabe Pharma Corporation

- QTcF \leq 450 msec

- HR \leq 50 bpm

- HR \geq 120 bpm

- QRS \geq 120 msec

7.2 Analysis Visit Definitions

Week 96 of Study MT-1186-A03 or Week 48 of Study MT-1186-A04 is defined as Day 1 of this study. By-visit summaries will be based on analysis visit. Any data out of the window will not be used. If there are multiple data of the same item within a window, the latest data will be used for analysis.

Tests	Analysis visit	Nominal time point	Analysis time window
Vital signs 12-lead ECG	Week 24	24 weeks after initiation of study treatment	Nominal time point \pm 30D
Body weight ALSFRS-R C-SSRS	EOS/ET	At the end of the study and early discontinuation	Nominal time point will be used.

In this study, because Edaravone became commercially available and the study was terminated, no subjects reached Week 24. Based on this condition, the sponsor decided in the DRM held on 20 Sep that only "EOS/ET" is used for analyses.

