8.1.3 Unscheduled Visits

An unscheduled visit is defined as any visit to the Investigator site outside of the protocol specified time points due to safety reasons or when a repeated measurement is required (e.g., obvious measurement errors, measuring device failure, confirmation of out-of-range results), where the subject is seen by study personnel.

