10.4 Body Weight

Body weight will be measured and recorded in kilograms in the eCRF.

10.5 12-lead Electrocardiogram

A 12-lead ECG will be performed after the subject has rested for at least 5 minutes in a supine position. The ECG must include the following measurements: R wave to R wave (RR) interval, heart rate, QRS, QT, corrected QT interval by Bazett (QTcB), and corrected QT interval by Fridericia (QTcF).

The Investigator will perform an overall evaluation of the ECG for safety purposes and the recording in the eCRF will be reported as 'normal', 'abnormal CS', or 'abnormal NCS'.

Abnormalities of clinical significance will be reported as AEs. Repeat measurements will be performed if needed.

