15.3.2 Data Handling

15.3.2.1 Handling of Time Point Data in Analyses Performed by Measurement time Point (Analysis Visit Windows)

For the analyses performed for each measurement time point, the allowable range of data handling for the analysis will be specified as analysis visit window in the SAPs.

No data imputation will be performed using data from outside the allowable range. If multiple values are available within the allowable range for the endpoint in question, then the latest value will be analyzed.

15.3.2.2 Handling of Reference Values and Indeterminate Values for Clinical Laboratory Test Parameters

If laboratory test value or its reference is indeterminate due to a problem with the test sample, then this value will be handled as a missing value.

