8.2.2 Vital signs

Absolute values will be summarized for the following parameters by analysis visit.

- Systolic blood pressure (mmHg)
- Diastolic blood pressure (mmHg)
- Heart rate (beats/min)
- Respiratory Rate (beats/min)
- Body temperature (°C)

For overall evaluation, number and percentage will be presented by analysis visit.

All data (including overall evaluation) will be listed.

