8.2.5 Physical Examinations

Physical examination will be listed.

8.2.6 12-Lead ECGs

Absolute values will be summarized for the following parameters by analysis visit.

- RR (msec)
- Heart rate (beats/min)
- QRS (msec)
- QT (msec)
- QTcB (msec)
- QTcF (msec)

For overall evaluation, number and percentage will be presented by analysis visit. The percentage of subjects with values outside pre-defined limits will be summarized by analysis visit.

All data (including overall evaluation) will be listed.

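### The ECG outlier table has no worst-reading row, so outliers at unscheduled visits, or at EOS/ET with an in-range repeat under the same visit, are listed but not counted

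*SAP*

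**What the plan says.** SAP 7.1.3.3 sets the ECG limits: QTcF bands cut at 450, 480 and 500 msec, heart rate at or below 50 or at or above 120 bpm, and QRS at or above 120 msec. SAP 8.2.6 then states: "The percentage of subjects with values outside pre-defined limits will be summarized by analysis visit".

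SAP 7.2 decides which reading represents a visit. It says "Any data out of the window will not be used" and "If there are multiple data of the same item within a window, the latest data will be used for analysis". EOS/ET has no day range; readings are assigned to it by nominal visit. The section records that, "because Edaravone became commercially available and the study was terminated, no subjects reached Week 24", and that the data review meeting therefore kept EOS/ET alone for the analyses. Protocol 15.3.2.1 has the same selection rule: "If multiple values are available within the allowable range for the endpoint in question, then the latest value will be analyzed".

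Readings can arise outside that visit, or more than once within it. Protocol 8.1.3 describes unscheduled visits as those made "due to safety reasons or when a repeated measurement is required (e.g., obvious measurement errors, measuring device failure, confirmation of out-of-range results". Protocol 10.5, on the ECG, says: "Abnormalities of clinical significance will be reported as AEs. Repeat measurements will be performed if needed".

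The investigator's overall rating (normal, abnormal not clinically significant, abnormal clinically significant) follows the same visit rule. SAP 8.2.2 says: "For overall evaluation, number and percentage will be presented by analysis visit". SAP 8.2.3 (orthostatic vital signs) and 8.2.6 (ECG) say the same. All ECG and vital-sign data are also listed.

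**The concern.** An outlier table is normally read as showing how many subjects were ever seen beyond a limit. This one shows how many were beyond it at the last reading of one visit. No rule for the worst reading, or for any reading after dosing, appears anywhere in the SAP.

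The choice also runs against the SAP's own convention for adverse events, which are counted at maximum severity and maximum relationship (SAP 8.2.1), with missing values imputed to the worse category (SAP 7.3).

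ECG parameters and vital signs are named among the primary safety endpoints. With Week 24 dropped, one scheduled ECG after Day 1 remains. A QTcF above a SAP limit that the investigator judged not clinically significant, recorded at an unscheduled visit, would appear only as a line in a listing. SAP 7.1.3.2 attaches a flag to out-of-range laboratory values; no such flag is stated for ECG values. The table could then show no subject beyond a limit when the database holds one.

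**Working it through.** The plan states no figure on this point, so there is none to reproduce. The check applies the rules case by case and then sizes the effect.

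**1. Which recorded outliers reach the table** (SAP 7.2 and 8.2.6; Protocol 8.1.3 and 10.5)

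| Out-of-range reading recorded at | What follows | Counted in the EOS/ET row? |
|---|---|---|
| Unscheduled visit | EOS/ET reading in range | No |
| EOS/ET | In-range repeat filed under EOS/ET | No |
| EOS/ET | Out-of-range repeat filed under EOS/ET | Yes |
| EOS/ET | Repeat filed as an unscheduled visit, any result | Yes, the original stands |
| EOS/ET | No repeat | Yes |

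The first two rows are the gap. An any-reading count includes the subject in all five rows, so the EOS/ET count can never exceed it.

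**2. Size per subject.** The denominator is the analysis set (SAP 6.1), planned at about 30. The number actually enrolled is not given, so a range is shown.
- n = 20: 1/20 = 5.0 points
- n = 30: 1/30 = 3.3 points
- n = 40: 1/40 = 2.5 points

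The number of unscheduled or repeat ECGs is not given either, so the total effect starts at zero.

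**3. Same-visit repeats, illustration only.** Assume a subject near a limit, each reading exceeding it independently with probability p, and a repeat filed under EOS/ET only after an exceedance. The latest-value rule counts the subject with probability p × p. An any-reading rule counts the subject with probability at least p.
- p = 0.1: 1% against 10%
- p = 0.3: 9% against 30%
- p = 0.5: 25% against 50%

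**4. Where the retained reading falls in the cycle.** The ten doses fall within days 1 to 14 of a 28-day cycle (Protocol 12.2), so the last dose is on day 10 to 14. Protocol 8.1.2 places EOS at the end of the last cycle when commercial drug becomes available.
- EOS on day 28: 28 − 14 = 14 to 28 − 10 = 18 days after the last dose
- With the ±7-day window of Table 1: 14 − 7 = 7 to 18 + 7 = 25 days
- ET is due within 7 days of discontinuation, so 0 to 7 days after the last dose if the subject stops on a dosing day
- Note b of the study schema asks for the EOS visit with no end-of-cycle condition, so that reading may also be closer to a dose

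**5. What a worst-reading row does to noise.** With 30 subjects, two independent readings each and a 2% outlier rate per reading (assumed), the expected number flagged is 30 × 0.02 = 0.60 from the latest reading and 30 × (1 − 0.98²) = 1.19 from either.

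**The case against.** The strongest reply is that the SAP follows the protocol. Protocol 15.3.2.1 sets the latest-value rule and Protocol 15.3.3.4 plans these summaries by visit; the SAP added the outlier limits. The study is single-arm and descriptive, using a confirmatory repeat is defensible, and worst-value counts pick up noise. All readings are listed, clinically significant abnormalities become adverse events and are tabulated, and with about 30 subjects the listing can be read in full. Nothing shows that even one affected reading exists, and Protocol 8.1.3 does not say that an unscheduled visit includes an ECG. All of this stands. It limits the point to the summary of outliers judged not clinically significant, and it is why the EOS/ET row should stay.

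A reader might infer more than the documents support:
- *That every repeated EOS/ET outlier is lost.* Only an in-range repeat under the same visit label displaces the original.
- *That the table shows only readings 14 to 18 days off drug.* That interval is nominal for EOS under Protocol 8.1.2. It does not hold for ET, for EOS called under schema note b, or at the edges of the ±7-day window.
- *That the SAP removes ECGs taken near dosing.* After Day 1, scheduled ECGs exist only at Week 24 and EOS/ET, so the timing comes from the visit schedule. An added row cannot create readings that were not taken.
- *That the outlier row is the only ECG summary free of investigator judgement.* SAP 8.2.6 also summarises RR, heart rate, QRS, QT, QTcB and QTcF, with minimum and maximum (SAP 6.1), under the same visit rule.

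**Conclusion.** The point holds as a gap in one kind of summary. Compared with a count over all readings after the first dose, the EOS/ET row can only be equal or lower. It omits outliers seen only at unscheduled visits and those displaced by an in-range repeat under the same visit. Each omitted subject is worth about 3.3 points at n = 30, enough to turn a one into a zero; the number omitted is unknown and may be zero. Data capture and adverse-event reporting are unaffected.

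This rests on reading the nominal-visit rule for EOS/ET as assignment by visit label, and on the data review decision in SAP 7.2. SAP 9.2 still lists Day 1 and Week 24 as reporting visits, so the restriction to EOS/ET comes from 7.2 alone. The change is a cheap improvement to a primary safety display; the EOS/ET row remains valid for what it measures.

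**What to change.** In SAP 7.2 and 8.2.6, keep the EOS/ET row and add one labelled *any reading after first dose in this study*. Use scheduled, unscheduled and repeat ECGs. Count each subject once, in the worst category: for QTcF the highest band reached, and for each heart-rate and QRS limit once if any reading meets it. Leave out readings documented as measurement error or device failure where that is recorded; the documents do not say whether the eCRF captures the reason for a repeat. Show the number of readings per subject beside the new row.

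Add the same row to the overall-evaluation counts for ECG, vital signs and orthostatic vital signs, ranking clinically significant above not clinically significant above normal.

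The cost is one row in four tables, from data already collected and listed, with no new visits or tests. The downside is that worst-value counts rise with noise and with more readings, which is why the EOS/ET row and the reading counts belong alongside. The fix does not change when ECGs were taken relative to dosing. If the data are already fixed, report the row as an ad-hoc analysis described in the CSR, as Protocol 15 provides.

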12.5 Procedures for Assigning Subjects to Treatment Groups

This is an open-label study. Therefore, no randomization or blinding is applicable. This

is a single-arm study without randomization.

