15.1 Determination of Sample Size

The study sample size is not based on power and statistical considerations. This study serves as an extension to MT-1186-A03 and MT-1186-A04 (the Parent study) and as such will roll over subject to the current study. The total number of subjects enrolled will depend on the number of subjects who complete Week 96 of Study MT-1186-A03 or Week48 of Study MT-1186-A04 and are also eligible and consent to participate in this extension study.

Approximately 30 patients will potentially be enrolled in this study.

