8.2.7 Body weight

Absolute values will be summarized and listed by analysis visit.

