9.2 Visit to Report

Visit for TFLs:

- Day 1
- Week 24
- EOS/ET

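### SAP 7.2 and 9.2 disagree on which visits are reported, and on either reading no within-subject change from Day 1 is summarised for body weight, vital signs or ECG

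*SAP*

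**What the plan says.** **Design and size.** The study "is a single-arm study without randomization" (Protocol 12.5). On size, "The study sample size is not based on power and statistical considerations"; "Approximately 30 patients will potentially be enrolled in this study" (Protocol 15.1).

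**Endpoints.** Protocol 5.2.1 counts body weight, ECG, vital signs and orthostatic vital signs among the primary safety endpoints.

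**Visits.** SAP 7.2 begins: "Week 96 of Study MT-1186-A03 or Week 48 of Study MT-1186-A04 is defined as Day 1 of this study". Its window table then covers only Week 24 and EOS/ET. After noting that nobody reached Week 24, it records that "the sponsor decided in the DRM held on 20 Sep that only 'EOS/ET' is used for analyses". SAP 9.2, under "Visit for TFLs", lists Day 1, Week 24 and EOS/ET.

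**Summaries.** For vital signs (SAP 8.2.2): "Absolute values will be summarized for the following parameters by analysis visit". Orthostatic vital signs (8.2.3) and ECG (8.2.6) are worded the same way. For body weight (8.2.7): "Absolute values will be summarized and listed by analysis visit". Vital signs and ECG also get counts of the investigator's overall rating. ECG gets the share of subjects beyond the QTcF, heart rate and QRS thresholds set in SAP 7.1.3.3. Individual data are listed. SAP 7.1 defines no change variable, and section 8 contains no change summary or shift table. Protocol 15.3.3.4 likewise plans summaries of values by visit only.

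**The concern.** With no control arm, an obvious summary of what happened to these measures during the study sets each subject's last value against that subject's own Day 1 value. The schedule takes the Day 1 value from the final parent-study visit, so no new measurement is needed.

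A mean weight, heart rate or QTcF at one visit reflects mainly who is in the study. It does not show whether the measure moved. A count of abnormal ratings or long QTcF values at one visit treats a finding already present on Day 1 the same as a new one.

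Two things are at stake. Two programmers following different SAP sections could produce different tables. And these measures would contribute less to the long-term safety objective than the collected data allow.

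**Working it through.** The plan states no SD, correlation, effect size or power, so it has no figure to reproduce. The check is mainly textual, followed by an illustration.

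**1. Which visits appear?**

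| Source | Day 1 | Week 24 | EOS/ET |
|---|---|---|---|
| SAP 7.2 window table | no row | row | row |
| SAP 7.2 decision after data review | not mentioned | dropped | kept |
| SAP 9.2 | listed | listed | listed |

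Week 24 conflicts outright. Day 1 conflicts if the 7.2 decision is read literally, because section 8 summarises by analysis visit and 7.2 gives Day 1 no analysis-visit row. The decision can also be read as choosing between the two post-baseline windows, which leaves Day 1 in the tables.

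**2. What does each reading deliver?**

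- *7.2 taken literally:* one column, EOS/ET. Change cannot be estimated from the summaries.
- *9.2 governs:* two columns, Day 1 and EOS/ET. With complete pairs, mean(EOS/ET) − mean(Day 1) = mean(EOS/ET − Day 1), so the mean change can be read off. With incomplete pairs the columns describe different subjects and this identity fails. The spread of change cannot be recovered either way. With equal column SDs it is SD × √(2(1 − r)), and the within-subject correlation r is not reported. Two columns with SD 12 kg fit any SD of change from 0 (r = 1) to 12 × √2 = 17.0 kg (r = 0).

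**3. Do the other outputs fill the gap?** Rating counts and ECG threshold percentages are totals at a visit. At EOS/ET alone, a QTcF above 450 msec that was there on Day 1 counts the same as a new one. With both visits shown, only the net difference is visible. Body weight has neither a rating nor a threshold.

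**4. Illustration for body weight.** Inputs: n = 30 (planned number, Protocol 15.1); SD = 12 kg and r = 0.95 to 0.99 (assumptions).

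- Standard error (SE) of the EOS/ET mean: 12/√30 = 2.19 kg.
- SE of the difference if the columns are treated as unpaired: 12 × √(2/30) = 3.10 kg.
- SD of paired change: 12 × √(2 × 0.05) = 3.79 kg at r = 0.95; 12 × √(2 × 0.01) = 1.70 kg at r = 0.99.
- SE of mean paired change: 3.79/√30 = 0.69 kg; 1.70/√30 = 0.31 kg.

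**5. Sensitivity to r, in SD units.** The 95% half-width for a single-visit mean with n = 30 is 0.373 SD. For the mean paired change it is that value times √(2(1 − r)):

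| r | Half-width (SD) |
|---|---|
| 0.5 | 0.373 |
| 0.7 | 0.289 |
| 0.8 | 0.236 |
| 0.9 | 0.167 |
| 0.95 | 0.118 |
| 0.98 | 0.075 |

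At r = 0.5 the paired change is no more precise than the single-visit mean. That mean, however, does not estimate change at all.

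**The case against.** The strongest defence is that 7.2 defines Day 1, sets windows for the two later visits, and gives the absence of Week 24 data as the reason for its decision. In that context, restricting to EOS/ET chooses between the two later visits. Day 1 is carried over and may need no window, and 9.2 lists it. On this reading the inconsistency is a leftover Week 24. This reading is reasonable, but the text does not settle it.

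A reader might infer that change is never shown, that absolute values are all that is planned, or that a shift in the mean would be invisible. The documents do not support these. Ratings and ECG thresholds are summarised, so absolute values stand alone only for body weight. Individual data are listed, and with about 30 subjects change can be worked out by hand wherever Day 1 is included. Abnormalities judged clinically significant are reported as AEs (Protocol 10.2, 10.3 and 10.5) and reach the TEAE tables if treatment-emergent. Under 9.2 with complete pairs, the two means differ by exactly the mean change. Nor is Day 1 the only reference, since the thresholds and the investigator's judgement are others.

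It is also true that the SAP does not depart from the protocol here. Protocol 5.2.2 names change from baseline as an endpoint only for ALSFRS-R, and the study is descriptive, with no planned comparison. So this is a better summary the plan could adopt, not a broken commitment.

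What remains is that listings are not a summary, AE reporting misses movements not judged clinically significant, and no planned table gives within-subject spread or new abnormalities.

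**Conclusion.** The point holds, with moderate weight. SAP 7.2 and 9.2 need reconciling: clearly for Week 24, and for Day 1 unless 7.2 is clarified. Under either reading, no change from Day 1 is summarised for body weight, vital signs (including orthostatic) or ECG.

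The loss depends on the reading: all information on change in the summaries if 7.2 is literal; the spread of change and the identification of new abnormalities if 9.2 governs. The kilogram figures rest on an assumed SD and a high assumed correlation. They illustrate body weight only and should not be carried over to heart rate, blood pressure or QTcF.

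A reader might also infer that paired change would reveal the effect of continued treatment. It would not. Subjects enter from earlier oral edaravone studies, so Day 1 is an on-treatment value. Protocol 4.2 describes A02 and A04 as comparing a daily with an on/off regimen, so some subjects may change regimen on entry. The disease also progresses. Paired change describes movement during A-301 and nothing more specific.

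**What to change.** - **SAP 7.2:** state that Day 1 (the parent-study Week 96 or Week 48 value) is kept as the reference visit and that EOS/ET is the only post-baseline visit.
- **SAP 9.2:** delete Week 24.
- **SAP 8.2.2, 8.2.3, 8.2.6 and 8.2.7:** add change from Day 1 to EOS/ET (n, mean, SD, median, minimum, maximum) for subjects with both values.
- **Shift tables:** add Day 1 by EOS/ET tables for the investigator ratings (vital signs, orthostatic vital signs, ECG) and for the ECG threshold categories.
- **SAP section 10:** record these additions, and describe the results as movement during A-301.

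**Cost.** A little programming and no new measurement. Day 1 parent-study values must be brought into the A-301 dataset if they are not already there. This should be checked: section 10 says the death, tracheostomy and ventilation data are collected only at EOS/ET, although the schedule also marks them at Day 1 as a carried-over item. If the data have already been fixed, Protocol section 15 provides for describing departures from the planned analysis in the CSR.
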